#### **Exceptions for data collection/recording on case report forms:**

- Only clinically significant vital sign abnormalities and lab results will be reported as Adverse Events

Abbreviated Title: BGJ398 in TIO

Version Date: 21MAY2019

- Individual lab values for general safety and monitoring will not be recorded in eCRF, unless clinically significant or relate to a protocol specific outcome as listed below. NIH or outside facility lab reports should be referenced results and will serve as source documentation. Date, time and designation of “significance” will be recorded in eCRF for all lab tests recorded. The following individual lab values will be recorded directly on the eCRF:
  - o FGF23
  - o TRP
  - o TmP/GFR

## 6.2 DATA SHARING PLANS

### 6.2.1 Human Data Sharing Plan

For future research collaborations the Principal Investigator will seek NIH IRB review and approval for sending coded data to non-NIH investigator(s). The principal investigator will identify the names of the collaborating researchers and their affiliated institutions, as well as intended plans for use at the time of submission.

The current plan for data sharing is as follows:

#### What data will be shared?

I will share human data generated in this research for future research as follows (*check all that apply*):

De-identified data in BTRIS (automatic for activities in the Clinical Center)

De-identified or identified data with approved outside collaborators under appropriate agreements

#### How and where will the data be shared?

Data will be shared through (*check all that apply*):

BTRIS (automatic for activities in the Clinical Center)

Approved outside collaborators under appropriate individual agreements.

Publication and/or public presentations.

#### When will the data be shared? (*check all that apply*)

Before publication.

At the time of publication or shortly thereafter.

*Abbreviated Title: BGJ398 in TIO*

*Version Date: 21MAY2019*

### **6.2.2 Genomic Data Sharing Plan: Not Applicable.**

## **6.3 RESPONSE CRITERIA**

For the purposes of this study, patients should be re-evaluated for response every 4 weeks  $\pm$  3 days.

Response and progression will be evaluated by biochemical evaluation (FGF23, mineral panel, 1, 25-(OH)2 levels, alkaline phosphatase, TRP, TmP/GFR) every 2 weeks  $\pm$  3 days.

### **Definitions**

Evaluable for toxicity: All patients will be evaluable for toxicity from the time of their first treatment with BGJ398.

Evaluable for objective response: The objective response is primarily determined by biochemical changes. All subjects will have, as part of the inclusion criteria, elevated plasma FGF23 and low phosphorous levels. A change in FGF23 and phosphorous levels will be used to evaluate the objective response.

Evaluable Non-Target Disease Response: Not applicable to our protocol as some of our patients have no tumor identified. We evaluate the efficacy of BGJ398 based on biochemical parameters.

### **6.3.1 Disease Parameters**

Measurable disease: The disease is measured in terms of biochemical parameters (FGF23, mineral panel, 1, 25-(OH)2-Vitamin D, 25-OH-Vitamin D, alkaline phosphatase, TRP, TmP/GFR every 2 weeks  $\pm$  3 days.

Non-measurable disease.: Not applicable.

Target lesions. Not applicable.

Non-target lesions: Not Applicable.

### **6.3.2 Methods for Evaluation of Measurable Disease**

All baseline evaluations will be performed as closely as possible to the beginning of treatment and never more than 1 week  $\pm$  4 days before the beginning of the treatment.

The labs done in between NIH visits will be done at the patient's local laboratories; at these local laboratories, only C-terminal FGF23 will be measured as intact FGF23 is not commercially available. Both intact and C-terminal FGF23 levels will be measured by ELISA (Immutopics, Athens, OH and Mayo Medical Laboratories, Rochester, MN) after each NIH visit. We will compare the off-drug levels of FGF23 and blood phosphorous levels with that of baseline levels for evaluating the efficacy of the drug.

### **6.3.3 Response Criteria**

#### **6.3.3.1 Evaluation of Target Lesions: Not Applicable.**

Complete Response (CR): Not applicable.

Partial Response (PR): Not applicable.

*Abbreviated Title: BGJ398 in TIO*

*Version Date: 21MAY2019*

Progressive Disease (PD): Not applicable.

Stable Disease (SD): Not applicable.

### **6.3.3.2 Evaluation of Non-Target Lesions**

Complete Response (CR): Normal FGF23 and phosphorous levels off drug are considered as complete metabolic response (CR).

Non-CR/Non-PD: Off drug decrease in FGF23 levels by 50% but still greater than the upper limit of the normal range and increase in plasma phosphorous levels by 50% but not to the normal range is considered as partial metabolic response.

Progressive Disease (PD): Increase in FGF23 levels, and decreased phosphorous levels (compared to that of baseline), off the drug is considered a progressive disease.

### **6.3.3.3 Evaluation of Best Overall Response**

Best overall response is determined in terms of FGF23 levels and blood phosphorous levels at the end of 9 months (6 months on drug and 3 months off the drug).

Complete Response (CR): Normal FGF23 and phosphorous levels are considered as complete metabolic response (CR).

Non-CR/Non-PD: Off drug decrease in FGF23 levels by 50% but still greater than the upper limit of the normal range and increase in plasma phosphorous levels by 50% but not to the normal range is considered as partial metabolic response.

Progressive Disease (PD): Increase in FGF23 levels, and decreased phosphorous levels (compared to that of baseline), off the drug is considered a progressive disease.

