## 7.2 NCI-IRB REPORTING

### 7.2.1 NCI-IRB Expedited Reporting of Unanticipated Problems and Deaths

The Protocol PI will report to the NCI-IRB:

- All deaths, except deaths due to progressive disease
- All Protocol Deviations
- All Unanticipated Problems
- All non-compliance

Reports must be received by the NCI-IRB within 7 working days of PI awareness via iRIS.

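### Progressive disease is called on any rise in FGF23 with any fall in phosphorus, with no margin or confirmation, and no category covers a patient who is unchanged, discordant or improved by less than 50%.

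*Combined protocol and SAP*

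**What the plan says.** Section 6.3 states that "Response and progression will be evaluated by biochemical evaluation". Section 6.3.3.3 then gives three classes and fixes the time: "Best overall response is determined in terms of FGF23 levels and blood phosphorous levels at the end of 9 months".

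- **Complete response:** normal FGF23 and normal phosphorus.
- **Non-CR/Non-PD**, which the text equates with partial metabolic response: "Off drug decrease in FGF23 levels by 50% but still greater than the upper limit of the normal range", together with a 50% rise in phosphorus that stays short of normal.
- **Progressive disease:** "Increase in FGF23 levels, and decreased phosphorous levels (compared to that of baseline), off the drug is considered a progressive disease".

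Section 6.3.3.2 repeats the partial and progressive definitions without a time point. The only mention of a stable class is "Stable Disease (SD): Not applicable", under target lesions in section 6.3.3.1, where every other class is also marked not applicable.

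On the reference value, section 6.3.2 says "We will compare the off-drug levels of FGF23 and blood phosphorous levels with that of baseline levels". It gives no rule for choosing or averaging baseline values, although the schedule of events draws FGF23 at both screening and V0. The same section says "Both intact and C-terminal FGF23 levels will be measured by ELISA", and the progression rule does not say which assay counts.

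**The concern.** The rule is lopsided. Partial response needs a 50% change in each marker, while progression needs only that one marker reads higher and the other lower, by any amount. A patient whose disease returns exactly to its pre-drug state has an even chance of each, so some such patients will be recorded as progressing when nothing has changed.

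The remaining unchanged patients, those whose markers move in conflicting directions, and those who improve by less than 50% fit none of the three classes. This gap needs no statistical assumption. The class whose name should mean everything else is defined as a response.

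At stake is the best overall response table of a 10-patient study. It could show progression after an experimental drug in patients who did not progress, and leave others with no entry.

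**Working it through.** **The plan's own figure.** There is none for misclassification. Table 8.4 gives exact limits for the complete response rate and is not an input here.

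**Inputs from the documents.** The progression rule (6.3.3.2, 6.3.3.3); one rating at month 9 (6.3.3.3); 10 patients and a hypothesized 40–60% effectiveness (8.5).

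**Assumptions.** The documents give neither the correlation r between the noise in the two changes nor any within-patient variation. Both are shown as ranges.

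**Step 1: no true change, one comparison.** Treat the two changes from baseline as bivariate normal with mean zero and correlation r. Then

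P(FGF23 up and phosphorus down) = 1/4 − arcsin(r)/(2π).

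For r = −0.5, arcsin(−0.5) = −0.5236, so P = 0.25 + 0.5236/6.2832 = 0.333.

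| r | P(progression label) |
|---|---|
| +0.5 | 16.7% |
| 0 | 25.0% |
| −0.3 | 29.8% |
| −0.5 | 33.3% |
| −0.8 | 39.8% |
| −0.9 | 42.8% |

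No variance appears in the formula. Under this model a more precise assay does not lower the rate; only a margin or a confirmation rule does.

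**Step 2: departures from the model.** First figure r = 0, second r = −0.5.

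- Phosphorus reported to 0.1 mg/dL (assumed true level 1.5–2.0 mg/dL, CV 5–15%; simulation): 16–23%; 23–31%. Ties account for the drop.
- Residual benefit of 0.5 SD of the change in both markers: 9.5%; 16.3%.
- Phosphorus alone raised by 1 SD of its change, as restarted supplements might do: 7.9%; 12.7%.

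**Step 3: effect of a margin on both markers,** in SDs of the change, for a patient truly at baseline.

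| Margin | r = 0 | r = −0.5 | r = −0.8 |
|---|---|---|---|
| none | 25% | 33% | 40% |
| 1 SD | 2.5% | 6.3% | 9.8% |
| 1.645 SD | 0.25% | 1.2% | 2.5% |
| 1.96 SD | 0.06% | 0.46% | 1.1% |

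**Step 4: a 50% margin on FGF23 alone,** phosphorus merely below baseline, no confirmation. With log-normal variation the threshold in SDs is ln(1.5) / √(2 ln(1 + CV²)), which is 2.87, 1.45 and 0.98 for assumed CVs of 10%, 20% and 30%. The false label rates for r = 0 to −0.5 are 0.1–0.2%, 4–6% and 8–13%. A borrowed 50% margin is therefore adequate only if FGF23 varies little within a patient.

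**The case against.** The strongest reply is that the label touches almost nothing.

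- **No planned analysis uses it.** Sections 8.3 and 8.4 analyse complete response and complete plus partial response. Every patient is a responder or not, and missing status counts as failure. Progression-free survival is not applicable (6.3.5). Progression is not among the removal criteria in 3.10.1 or the extension criteria in 3.1.3. This stands in full.
- **Few reverting patients reach the month-9 rating off drug.** Under 3.1, 3.1.3 and 6.3.4, off-drug follow-up is for apparent complete responders. Others are offered the extension, if phosphate normalized on drug, or are referred. This largely stands. However, 6.3.3.2 has no time point, so a label at the end-of-treatment draws is not ruled out, and the extension is only an offer.
- **The rate is conditional.** It needs zero true change, continuous readings and a value of r that the documents do not give. Under 3.1, supplements are withheld before the first dose but may be restarted off drug, which works against a fall in phosphorus. This stands.

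Four stronger readings are tempting, and the documents support none of them.

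1. *A quarter to a third of reverting patients will be mislabelled.* That is simply the range r = 0 to −0.5 under the ideal conditions of Step 1.
2. *One or two of the ten will be falsely progressive.* The sum is 4 × 0.25 = 1 to 6 × 1/3 = 2, but it requires every hypothesized non-responder to return exactly to baseline and still be rated off drug.
3. *The false rate is 48–58%.* That follows if progression may be called at any of three off-drug visits (r = 0 to −0.5). Section 6.3.3.3 uses month 9 only.
4. *The label governs safety reporting.* Section 7.2.1 lists for reporting "All deaths, except deaths due to progressive disease", and 3.1.1 sets aside events attributed to disease progression. Both are judgements about the cause of an event, and neither refers to 6.3.3. An off-drug laboratory label does not make a death due to progression.

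**Conclusion.** The point holds as a defect in the response definitions, with limited reach. Two parts rest on the text alone: progression has no margin or confirmation, and unchanged, discordant or slightly improved patients have no category. The size rests on assumptions: 25% at r = 0 and 33% at r = −0.5 for a patient with exactly zero true change, continuous readings and a single comparison. Realistic departures mostly lower it.

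The effect is confined to the descriptive best overall response label. The primary endpoint and the section 8 rates are unaffected. It should still be corrected, because the protocol says it will determine this classification and the rule as written can give wrong labels.

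**What to change.** In both 6.3.3.2 and 6.3.3.3:

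1. Require the FGF23 rise and the phosphorus fall each to exceed a prespecified margin based on the within-patient variation of the change. For FGF23, the 50% margin already used for partial response is an alternative, subject to Step 4.
2. State which baseline value is used, or how values are combined. Name the FGF23 assay too, since the margin depends on it.
3. Confirm on a second off-drug draw from the same period. For a rating at week 24/25, use the daily draws of section 3.4. For a month-9 rating, use the scheduled 4-weekly off-drug visits where available. The section 3.4 draws (up to seven, in the week after the last dose) cannot confirm a month-9 rating.
4. Add a no response/stable category for everyone not otherwise classified.

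The cost is protocol and analysis wording, plus assay variation data from the sponsor to set the margins. No new sampling visits are needed where the patient remains off drug on study. The downside is slightly less sensitivity to small true worsening.

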### **6.3.4 Duration of Response**

Duration of overall response: If complete metabolic response is achieved at the end of the 1 week end-of-study pharmacodynamic period (see section 3.4) following 24 weeks of BGJ398, the subjects will be followed for an additional 11 weeks ( $\pm$  2 weeks). If the subject has not had complete metabolic response at the end the 1 week end-of-study pharmacodynamic period or at any time during the follow-up, he/she will be offered the option of entering the extension phase or referred for alternative treatments.

### **6.3.5 Progression-Free Survival: Not Applicable.**

### **6.3.6 Response Review: Not applicable.**

## **6.4 TOXICITY CRITERIA**

The descriptions and grading scales found in the revised NCI Common Terminology Criteria for Adverse Events (CTCAE) version 4.0 will be utilized for AE reporting.

## 7 SAFETY REPORTING REQUIREMENTS/DATA AND SAFETY MONITORING

### 7.1 DEFINITIONS

#### Adverse Event

An adverse event is defined as any reaction, side effect, or untoward event that occurs during the course of the clinical trial associated with the use of a drug in humans, whether or not the event is considered related to the treatment or clinically significant. For this study, AEs will include events reported by the patient, as well as clinically significant abnormal findings on physical examination or laboratory evaluation. A new illness, symptom, sign or clinically significant laboratory abnormality or worsening of a pre-existing condition or abnormality is considered an AE. All AEs must be recorded on the AE case report form. All AEs, including clinically significant abnormal findings on laboratory evaluations, regardless of severity, will be followed until return to baseline or stabilization of event. Serious adverse events that occur more than 30 days after the last administration of investigational agent/intervention and have an attribution of at least possibly related to the agent/intervention should be recorded and reported as per sections 7.2, 7.4, 7.5.

An abnormal laboratory value will be considered an AE if the laboratory abnormality is characterized by any of the following:

- Results in discontinuation from the study
- Is associated with clinical signs or symptoms
- Requires treatment or any other therapeutic intervention
- Is associated with death or another serious adverse event, including hospitalization.
- Is judged by the Investigator to be of significant clinical impact
- If any abnormal laboratory result is considered clinically significant, the investigator will provide details about the action taken with respect to the test drug and about the patient's outcome.

#### Suspected adverse reaction

Suspected adverse reaction means any adverse event for which there is a reasonable possibility that the drug caused the adverse event. For the purposes of IND safety reporting, 'reasonable possibility' means there is evidence to suggest a causal relationship between the drug and the adverse event. A suspected adverse reaction implies a lesser degree of certainty about causality than adverse reaction, which means any adverse event caused by a drug.

#### Unexpected adverse reaction

An adverse event or suspected adverse reaction is considered "unexpected" if it is not listed in the investigator brochure or is not listed at the specificity or severity that has been observed; or, if an investigator brochure is not required or available, is not consistent with the risk information described in the general investigational plan or elsewhere in the current application. "Unexpected" also refers to adverse events or suspected adverse reactions that are mentioned in the investigator brochure as occurring with a class of drugs or as anticipated from the pharmacological properties of the drug, but are not specifically mentioned as occurring with the particular drug under investigation.

#### Serious

*Abbreviated Title: BGJ398 in TIO*

*Version Date: 21MAY2019*

An Unanticipated Problem or Protocol Deviation is serious if it meets the definition of a Serious Adverse Event or if it compromises the safety, welfare or rights of subjects or others.

### **Serious Adverse Event**

An adverse event or suspected adverse reaction is considered serious if in the view of the investigator or the sponsor, it results in any of the following:

- Death,
- A life-threatening adverse drug experience
- Inpatient hospitalization or prolongation of existing hospitalization
- Persistent or significant incapacity or substantial disruption of the ability to conduct normal life functions
- A congenital anomaly/birth defect.
- Important medical events that may not result in death, be life-threatening, or require hospitalization may be considered a serious adverse drug experience when, based upon appropriate medical judgment, they may jeopardize the patient or subject and may require medical or surgical intervention to prevent one of the outcomes listed in this definition.

### **Disability**

A substantial disruption of a person's ability to conduct normal life functions.

### **Life-threatening adverse drug experience**

Any adverse event or suspected adverse reaction that places the patient or subject, in the view of the investigator or sponsor, at immediate risk of death from the reaction as it occurred, i.e., it does not include a reaction that had it occurred in a more severe form, might have caused death.

### **Protocol Deviation**

Any change, divergence, or departure from the IRB-approved research protocol.

### **Non-compliance**

The failure to comply with applicable NIH Human Research Protections Program (HRPP) policies, IRB requirements, or regulatory requirements for the protection of human research subjects.

### **Unanticipated Problem**

Any incident, experience, or outcome that:

- Is unexpected in terms of nature, severity, or frequency in relation to
  - (a) the research risks that are described in the IRB-approved research protocol and informed consent document; Investigator's Brochure or other study documents, and
  - (b) the characteristics of the subject population being studied; **AND**
- Is related or possibly related to participation in the research; **AND**

Abbreviated Title: BGJ398 in TIO

Version Date: 21MAY2019

- Suggests that the research places subjects or others at a *greater risk of harm* (including physical, psychological, economic, or social harm) than was previously known or recognized.

## 7.2 NCI-IRB REPORTING

### 7.2.1 NCI-IRB Expedited Reporting of Unanticipated Problems and Deaths

The Protocol PI will report to the NCI-IRB:

- All deaths, except deaths due to progressive disease
- All Protocol Deviations
- All Unanticipated Problems
- All non-compliance

Reports must be received by the NCI-IRB within 7 working days of PI awareness via iRIS.

### 7.2.2 NCI-IRB Requirements for PI Reporting at Continuing Review

The protocol PI or designee will report to the NCI-IRB:

1. A summary of all protocol deviations in a tabular format to include the date the deviation occurred, a brief description of the deviation and any corrective action.
2. A summary of any instances of non-compliance
3. A tabular summary of the following adverse events:
  - All Grade 2 **unexpected** events that are possibly, probably or definitely related to the research;
  - All Grade 3 and 4 events that are possibly, probably or definitely related to the research;
  - All Grade 5 events regardless of attribution;
  - All Serious Events regardless of attribution.

Principal Investigator or designee will use the summary table 7.2.2 to report of adverse events that have occurred on the protocol since the previous continuing review and in aggregate.

Table 7.2.2: Summary table of adverse events:

System Organ Class	CTCAE Term	Grade	# of Events since last CR	Total # of Events	Attribution to Research	Serious?	Unexpected?

### 7.2.3 NCI-IRB Reporting of IND Safety Reports

Only IND Safety Reports that meet the definition of an unanticipated problem will be reported to the NCI IRB.

### **7.3 NCI GUIDANCE FOR REPORTING EXPEDITED ADVERSE EVENTS FOR MULTI-CENTER TRIALS: NOT APPLICABLE**

### **7.4 IND SPONSOR REPORTING CRITERIA: NOT APPLICABLE**

### **7.5 FDA REPORTING CRITERIA**

#### **7.5.1 IND Safety Reports to the FDA**

The Sponsor will notify the FDA of any unexpected fatal or life-threatening suspected adverse reactions as soon as possible but no later than 7 calendar days of initial receipt of the information using the MedWatch Form 3500a.

The Sponsor is also responsible for reporting any:

- suspected adverse reaction that is both serious and unexpected
- any findings from clinical, epidemiological, or pooled analysis of multiple studies or any findings from animal or in vitro testing that suggest a significant risk in humans exposed to the drug
- clinically important increase in the rate of a serious suspected adverse reaction over that listed in the protocol or investigator brochure

to the FDA no later than 15 calendar days after determining that the information qualifies for reporting using the MedWatch Form 3500a. If FDA requests any additional data or information, the sponsor must submit it to the FDA as soon as possible, but no later than 15 calendar days after receiving the request.

#### **7.5.2 FDA Annual Reports**

Principal Investigator will submit a brief report annually of the progress of the trial within 60 days of the anniversary date that the IND went into effect as indicated in 21CFR 312.33, and any associated FDA correspondences regarding the IND annual report.

